7.1.3.2. Coding of grading for Solicited symptoms

The maximum intensity of local injection site redness or swelling will be graded at GSK Biologicals as follows:

- 0 : ≤ 20 mm
- 1 : > 20 to 50 mm
- 2 : > 50 to 100 mm
- 3 : > 100 mm

Body temperatures will be graded at GSK Biologicals as follows:

- 0 $< 38.0^{\circ}\text{C}$ ($< 100.4^{\circ}\text{F}$)
- 1 $\geq 38.0 - 38.4^{\circ}\text{C}$ ($\geq 100.4 - 101.2^{\circ}\text{F}$)
- 2 $\geq 38.5 - 38.9^{\circ}\text{C}$ ($\geq 101.3 - 102.1^{\circ}\text{F}$)
- 3 $\geq 39.0 - 40^{\circ}\text{C}$ ($\geq 102.2 - 104.0^{\circ}\text{F}$)
- 4 $> 40.0^{\circ}\text{C}$ ($> 104.0^{\circ}\text{F}$)

Fever is defined as temperature $\geq 38.0^{\circ}\text{C}/100.4^{\circ}\text{F}$. The preferred route for recording temperature in this study is axillary.

- For clinicaltrials.gov and EudraCT posting purposes, a summary of subjects with all combined solicited (regardless of their duration) and unsolicited adverse events will be provided. Solicited adverse events will be coded by MedDRA as per the following codes:

Solicited symptom	Lower level code	Lower level term
Pain at injection site	10022086	Injection site pain
Redness at injection site	10022098	Injection site redness
Swelling at injection site	10053425	Injection site swelling
Fever	10016558	Fever
Irritability/Fussiness	10057224	Irritability post vaccinal
Loss of appetite	10003028	Appetite lost
Drowsiness	10013649	Drowsiness

7.1.3.3. Onset day

The onset day for an event will be the number of days between the most recent vaccination and the start of the event. Events occurring on the day of vaccination will have an onset day of 0.

7.1.3.4. Duration of events

The duration of an event will be the number of days (not necessarily consecutive) with symptom during the solicited follow-up period.

7.2. Methodology for computing CI

All CI will be 2 sided 95% CI.

- The exact 95% CIs for a proportion within a group will be calculated from Proc StatXact [Clopper CJ, Pearson ES, 1934].
- The 95% CIs for GMT are obtained within each group separately. The 95% CI for the mean of lot-transformed titer is first obtained assuming that log-transformed titers are normally distributed with unknown variance. The 95% CI for the GMT is then obtained by exponential-transformation of the 95% CI for the mean of log-transformed titer.
- The group GMT ratio will be obtained using an ANCOVA model on the logarithm- transformed titers. The ANCOVA model will include the vaccine group as fixed effect and the pre-vaccination \log_{10} titer and, age as regressor. The GMT ratio and its 95% CI will be derived as exponential-transformation of the corresponding group contrast in the model.

7.3. Data presentation description:

The following decimal description from the decision rules will be used for the demography, immunogenicity and safety/reactogenicity.

Display Table	Parameters	Number of decimal digits
Demographic characteristics	Mean, median age	1
Demographic characteristics	SD (age)	1
Immunogenicity	Ratio of GMT	2
Reactogenicity	Mean, Min, Q1, Median, Q3, Max for duration	1
All summaries	% of count, including LL & UL of CI	1
All summaries	% of ratio, including LL & UL of CI	1

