## 4. STUDY COHORT

### 4.1. Number of subjects/centres

A total of approximately 185 subjects will be enrolled at multiple study centers

The estimated time to complete enrollment is approximately 3 months (the Sponsor may re-evaluate as needed). SBIR will be used to monitor progress against the recruitment plan. Enrollment will be terminated when approximately 185 subjects have been randomised/enrolled.

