##### **5.2.2.2.1. Study group and randomization/treatment number allocation**

Target enrolment for the study will be approximately 185 healthy children (6 to less than 36 months of age) who will be randomised into 5 groups (n=37 per group) in a 1:1:1:1:1 ratio (see [Figure 1](#)).

Allocation of the subject to a study group at the investigator site will be performed using a central randomisation system on the internet (SBIR). The randomisation algorithm will use a minimisation procedure accounting for age (6-<12 months; 12 – less than 36 months), study centre, and the pre-study seasonal influenza vaccine history the subjects to ensure balanced representation of the combination of the minimisation factors among the study groups.

After obtaining the signed and dated ICF from the subject and having checked the eligibility of the subject, the study staff in charge of the vaccine administration will access SBIR. Upon providing the subject's age and the subject identification number, the randomisation system will provide the treatment number to be used for each dose.

The number of each administered treatment must be recorded in the eCRF on the Vaccine Administration screen.

When SBIR is not available, please refer to the SBIR user guide or the Study Procedures Manual (SPM) for specific instructions.

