## 5.5. Outline of study procedures

**Table 6 List of study procedures**

Type of contact	Epoch 001					Epoch 002		
	Visit 1	Visit 2	Visit 3	Visit 4 (TC1)	Visit 5 (TC2)	Visit 6	Visit 7	Visit 8 (TC3)
Time point (s)	Day 0	Day 21	Day 42	Day 90	Day 240	Day 385	Day 392	Day 415
Sampling timepoint(s)	Pre-Vacc 1	Pre-Vacc 2	Post-Vacc 2			Post-Vacc 2	Post-Vacc 3	
Informed consent	●							
Check inclusion / exclusion criteria	●							
Check contraindications to vaccination *	●	●				●		
Medical history	●							
Seasonal influenza vaccination history 	●							
Collect demographic data	●							
Physical examination	●							
Measure/record height and weight	●							
Brief (symptom directed) physical examination		○	○			○	○	
Record concomitant medications and vaccinations	●	●	●	●	●	●	●	●
Pre-vaccination body temperature /vital signs	●	●				●		
Study group and treatment number allocation	●							
Treatment number allocation for subsequent doses		●				●		
Blood sampling for assessment of humoral immune response (approx. 2.5 mL venous blood)	●		●			●	●	
Blood sampling for assessment of CMI response (approx. 2.0 mL venous blood)	●		●			●	●	
Vaccine dose preparation by unblinded staff	○	○				○		
Vaccine administration (record treatment number)	●	●				●		
Provide training / Distribute diary cards 	○	○				○	○	
Parent/LAR records solicited AEs  (beginning on the day of the dose and for the following six days; e.g., Day 0 – 6)	○	○				○		
Parent/LAR records unsolicited AEs beginning with day of vaccination and continuing for next 20 (doses 1 and 2) or 29 (booster dose) days	○	○				○	○	○
Parent/LAR returns diary cards		○	○				○	

Type of contact	Epoch 001				Epoch 002			
	Visit 1	Visit 2	Visit 3	Visit 4 (TC1)	Visit 5 (TC2)	Visit 6	Visit 7	Visit 8 (TC3)
Time point (s)	Day 0	Day 21	Day 42	Day 90	Day 240	Day 385	Day 392	Day 415
Sampling timepoint(s)	Pre-Vacc 1	Pre-Vacc 2	Post-Vacc 2			Post-Vacc 2	Post-Vacc 3	
Investigator transcribes diary card data		●	●				●	●
Report all non-serious adverse events 	●	●	●			●	●	●
Report non-serious adverse events leading to study withdrawal	●	●	●	●	●	●	●	●
Report current/intercurrent medical conditions	●	●	●			●	●	●
Report medically attended events 	●	●	●	●	●	●	●	●
Report serious adverse events 	●	●	●	●	●	●	●	●
Report pIMDs 	●	●	●	●	●	●	●	●
Report SAEs related to study participation or GSK concomitant product or any fatal SAE	●	●	●	●	●	●	●	●
Study conclusion								●

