**Table 21 Lower limit of 95%CI for GMT ratio of vaccine group to the reference group 21- days after second vaccination**

	log GMT standard deviation				
	0.50	0.55	0.60	0.65	0.70
GMT ratio	0.25	0.14	0.13	0.13	0.12
	0.29	0.16	0.16	0.15	0.14
	0.34	0.19	0.18	0.17	0.16
	0.4	0.23	0.21	0.20	0.19
	0.5	0.28	0.27	0.25	0.24
	0.67	0.38	0.36	0.34	0.32
	1	0.57	0.54	0.51	0.48

Assumed non-evaluable rate is less than 10%, with a sample size of 34 evaluable subjects per group and SD (log value)=0.60, the LL of 95%CI for the GMT ratio would be 0.25 if the point estimate of GMT ratio of vaccine group to the reference group is 0.5 (50% of GMT value deduction).

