## 10.6.2. Analyses of primary objectives

### 10.6.2.1. Immunogenicity-fever indices

These analyses will be performed on the cohort described in Section 10.4.2.

An analysis of covariance model (ANCOVA) will be fitted on the  $\log_{10}$  transformed HI and MN antibody responses at Day 42, with the vaccine group as a fixed independent variable, adjusted by the  $\log_{10}$  transformed pre-vaccination titer and age. *(Amended: 27-MAR-2017)*

For **vaccine-homologous** HI and MN separately, an immunogenicity index ( $D_{GMT}$ ) will be constructed using a desirability function based on the computed GMT group ratio (alternative dose regimen to reference = 1.9  $\mu$ g HA with AS03B) and the 95%CI. *(Amended: 27-MAR-2017)*

- $D_{GMT}$  will be the LL of the 95% CI for GMT group ratio
  - If the LL of the 95% CI for GMT group ratio is less than 0.25 (i.e., 4- fold less than that of the reference group), then  $D_{GMT} = 0$ .
  - If the LL of the 95% CI for GMT group ratio is greater than 1 (comparison group has higher GMT value than the reference group),  $D_{GMT} = 1$ .

note  $D_{GMT} = 1$  for the reference group

The fever index ( $D_R$ ) will be calculated according to body temperature measurements performed from Days 0-2 after each dose

- Any temperature  $< 38^{\circ}\text{C}$  (100.4 F) will be assigned a value of 0. Any temperature  $> 40.5^{\circ}\text{C}$  will be assigned a value of 40.5).
- The highest possible temperature value per subject is 243 (6 x  $40.5^{\circ}\text{C}$ ; i.e. for 3 days after dose 1 and dose 2);
- The lowest possible temperature value per subject is 0 (all measurements  $< 38.0^{\circ}\text{C}$  (100.4 F) for 3 days after dose 1 and dose 2).
- For each subject, a temperature index will be constructed as follows: (243 minus the sum of recorded temperature values for 3 days after dose 1 and dose 2)/243. The average temperature measurement for each vaccine group will be calculated as the  $D_R$ . A lower index value  $D_R$  indicates a less desirable regimen in terms of reactogenicity.

An immunogenicity-fever index (D) at Day 42 will be computed for each group

$$D = \sqrt{D_{GMT} \times D_R}$$

This index (D) will range between 0 and 1 (0 = not desirable; 1 = highly desirable) and the same weight (0.5) is assigned for immunogenicity index and reactogenicity (fever) index.

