6.1.2.1. Immunogenicity/fever indices (Co-primary objectives)

An analysis of covariance model (ANCOVA) will be fitted on the \log_{10} transformed HI and MN antibody responses at Day 42, with the vaccine group as a fixed independent variable, adjusted by the \log_{10} transformed pre-vaccination titer and age.

For **vaccine homologous** HI and MN separately, an immunogenicity index (D_{GMT}) will be constructed using a desirability function based on the computed GMT group ratio (alternative dose regimen to reference = 1.9 μ g HA with AS03_B) and the 95% CI.

D_{GMT} will be the LL of the 95% CI for GMT group ratio

- If the LL of the 95% CI for GMT group ratio is less than 0.25 (i.e., 4- fold less than that of the reference group), then $D_{GMT} = 0$.
- If the LL of the 95% CI for GMT group ratio is greater than 1 (comparison group has higher GMT value than the reference group), $D_{GMT} = 1$.
note $D_{GMT} = 1$ for the reference group

The fever index (D_R) will be calculated according to body temperature measurements performed from Days 0-2 after each dose

- Any temperature $< 38^{\circ}\text{C}$ (100.4 F) will be assigned a value of 0. Any temperature $> 40.5^{\circ}\text{C}$ will be assigned a value of 40.5).
- The highest possible temperature value per subject is 243 (6 x 40.5°C ; i.e. for 3 days after dose 1 and dose 2);
- The lowest possible temperature value per subject is 0 (all measurements $< 38.0^{\circ}\text{C}$ (100.4 F) for 3 days after dose 1 and dose 2).
- For each subject, a temperature index will be constructed as follows: (243 minus the sum of recorded temperature values for 3 days after dose 1 and dose 2)/243. The average temperature measurement for each vaccine group will be calculated as the D_R . A lower index value D_R indicates a less desirable regimen in terms of reactogenicity.

An immunogenicity-fever index (D) at Day 42 will be computed for each group

$$D = \sqrt{D_{GMT} \times D_R}$$

This index (D) will range between 0 and 1 (0 = not desirable; 1 = highly desirable) and the same weight (0.5) is assigned for immunogenicity index and reactogenicity (fever) index.

Two immunogenicity-fever indices will be separately calculated for HI and MN **assay against vaccine-homologous virus**. Each will be used to rank the different dosing regimens as a tool to guide dosing regimen selection.

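### The Day 42 ANCOVA leaves out two of the three minimisation factors (study centre and seasonal influenza vaccination history), although its lower confidence limit is itself the immunogenicity score

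*SAP*

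**What the plan says.** Protocol 5.2.2.2.1 allocates by minimisation on age (6 to under 12 months, 12 to under 36 months), "study centre, and the pre-study seasonal influenza vaccine history the subjects to ensure balanced representation of the combination of the minimisation factors".

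The Day 42 model is narrower. Protocol 10.6.2.1 fits an ANCOVA on log10 titre "with the vaccine group as a fixed independent variable, adjusted by the" log10 pre-vaccination titre and age. SAP 6.1.2.1 repeats this, and SAP 7.2 states it again: "The ANCOVA model will include the vaccine group as fixed effect and the pre-vaccination" log10 titre and age. Neither document puts centre or vaccination history in the model, explains their absence or plans a sensitivity analysis with them.

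The lower limit of the resulting two-sided 95% interval for the GMT ratio is D_GMT. SAP 6.1.2.1 sets a floor: "If the LL of the 95% CI for GMT group ratio is less than 0.25", D_GMT is 0. It is capped at 1, and the reference group is given 1. The overall index is D = sqrt(D_GMT x D_R), calculated once for HI and once for MN.

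**The concern.** Balancing the groups on a prognostic factor makes the estimated group difference more precise. A model that omits the factor does not see that gain: the factor's variance stays in the residual, and the reported interval is wider than the allocation warrants.

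In most trials that would only be cautious. Here the lower limit is the score. Because the reference is fixed at 1, extra width can lower an alternative regimen but never the reference. Below 0.25 the score drops to zero, and D drops to zero with it, whatever the regimen gains on fever. The worked example in Protocol 10.3 lies at that floor: "the LL of 95%CI for the GMT ratio would be 0.25 if the point estimate of GMT ratio of vaccine group" to reference is 0.5. Since the trial asks whether the current paediatric formulation should be kept or modified, the error leans towards keeping it.

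**Working it through.** **Inputs.** From Protocol 10.3, Table 21 and its text: 34 evaluable subjects per group, SD 0.60 on the log10 scale, ratio 0.5, stated lower limit 0.25. From SAP 6.1.2.1: floor 0.25. Assumed, because the documents are silent: R2, the share of residual variance explained by centre and vaccination history together.

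**The protocol's own figure.** A two-sample interval on log10 titres gives LL = ratio x 10^(-t x SD x sqrt(2/n)).
- n = 34, df 66, t = 1.997: 0.5 x 10^(-1.997 x 0.60 x 0.2425) = 0.256.
- n = 33, df 64: 0.253. This matches all 28 legible cells of Table 21 to two decimals. The difference from 34 does not matter here.

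**Planned ANCOVA.** 170 subjects, five groups and two covariates give df = 170 - 5 - 2 = 163 and t = 1.9746. With 0.60 taken as the residual SD, SE = 0.60 x sqrt(2/34) = 0.1455 and LL = 0.5 x 10^(-1.9746 x 0.1455) = 0.258.

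**With the omitted factors removed from the residual.** SE becomes 0.1455 x sqrt(1 - R2). The ratio needed to clear the floor is 0.25 divided by the LL at ratio 1. The change in D is the square root of the ratio of the two limits, minus 1. The chance of a zero score is for a true ratio of 0.5, with a normal estimate whose SE reflects the balanced allocation; on that basis the planned model gives about 0.46 throughout.

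| R2 (assumed) | LL at ratio 0.5 | Change in D_GMT | Change in D | Ratio needed to clear 0.25 | Chance of D_GMT = 0 |
|---|---|---|---|---|---|
| 0 | 0.258 | – | – | 0.485 | 0.46 |
| 0.05 | 0.262 | +1.7% | +0.8% | 0.476 | 0.44 |
| 0.10 | 0.267 | +3.5% | +1.7% | 0.468 | 0.42 |
| 0.20 | 0.277 | +7.2% | +3.6% | 0.452 | 0.37 |

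The closed form charges nothing for the extra parameters, so it is an upper bound on the gain.

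**Simulation with that cost included.** 170 subjects in five arms, minimised on all three factors with probability 0.9 of the best arm; 40% with vaccination history; unequal centres; the effect split between centre and history; 600 trials. Mean LL at ratio 0.5:

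| Centres (assumed) | R2 | Planned model | History + all centres | History + centres, those under 10 pooled |
|---|---|---|---|---|
| 8 | 0 | 0.2579 | 0.2572 | 0.2574 |
| 8 | 0.10 | 0.2571 | 0.2651 | 0.2652 |
| 20 | 0 | 0.2578 | 0.2533 | 0.2569 |
| 20 | 0.05 | 0.2573 | 0.2577 | 0.2599 |
| 20 | 0.10 | 0.2575 | 0.2621 | 0.2635 |
| 20 | 0.20 | 0.2574 | 0.2725 | 0.2716 |

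With 20 centres and pooling, the gain in D_GMT is 1.0%, 2.3% and 5.5% at R2 of 0.05, 0.10 and 0.20 (for example, 0.2635/0.2575 = 1.023).

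**Is the planned interval really too wide?** A separate simulation with 12 centres and R2 = 0.20 gave a planned-model SE of 0.146 against an empirical SD of 0.131, with coverage 0.969. With the factors added, the SE was 0.132 and coverage 0.954. At R2 = 0 the planned model had nominal coverage.

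**The case against.** The facts are not in dispute; the size is.

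- **R2 is assumed.** Nothing in the documents says that centre or vaccination history predicts H5N1 titre. If they do not, adding them moves the limit slightly the wrong way. This stands, and it is why the finding is conditional. The loss is small: 0.258 to about 0.257 with pooling, 0.253 with 20 unpooled centres.
- **The closed form flatters the fix.** This stands too; the simulated gains are the better guide to what the fix delivers.
- **0.60 is treated as the residual SD**, although Table 21 uses it for an unadjusted comparison. If baseline titre and age explained 10% of the variance (an assumption), the planned limit would already be 0.267 and the example would sit further from the floor. Likewise, age may already carry part of the effect of vaccination history. Both points are fair.
- **Ratio 0.5 is one worked example**, not an expectation. At a true ratio of 1, with R2 = 0.10, the chance of a zero score only moves from 0.012 to 0.009. The floor therefore matters for regimens with clearly lower titres.
- **The error is conservative, comparisons are descriptive and there is no dose-selection algorithm.** All true, and the alternatives share one residual variance, so their order barely moves. But conservatism is not neutral when the lower limit is the score and the reference is exempt from it.

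**Conclusion.** The concern holds. Two of the three factors used to balance the groups are missing from the model that produces both co-primary immunogenicity scores, without a stated reason. The effect is modest and conditional. If the factors explain 5% to 20% of residual variance, D_GMT in the worked example is understated by at most about 2% to 7%, and by about 1% to 5.5% once the cost of 20 centres with pooling is counted. The chance that a regimen with a true ratio of 0.5 is scored zero is up to about 9 percentage points too high (46% against 37% at R2 = 0.20).

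What is affected is each alternative's standing against the reference, and whether one near the floor is scored zero. The results rest on an assumed R2, assumed numbers of centres (Protocol 4.1 says only "A total of approximately 185 subjects will be enrolled at multiple study centers") and a residual SD of 0.60. It should be changed, but it does not undermine the ranking of the alternatives.

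**What to change.** In Protocol 10.6.2.1 and SAP 6.1.2.1 and 7.2, add seasonal influenza vaccination history (yes/no, one degree of freedom) and study centre to the ANCOVA, beside log10 pre-vaccination titre and age. State in advance how small centres are handled: for example, centres with fewer than 10 subjects in the analysis cohort form one category, or centre is a random effect. If Day 42 results by group have already been seen, keep the planned model as primary, add this one as a sensitivity analysis specified before it is run, and report whether any D_GMT crosses 0.25. If the factors were left out on purpose, say why.

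The cost is a line in each document and in the model code. No new data are needed: centre is known, and "Seasonal influenza vaccination history" is already recorded at Visit 1 (Protocol Table 6). The statistical cost is a few degrees of freedom.

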7.4. Interpretation of analyses

In this study, all the comparative analyses will be descriptive with the aim to rank alternative dosing regimens with respect to immunogenicity and reactogenicity at Day 42, persistence at Day 385, and anamnestic response to unadjuvanted antigen booster dose at Day 392. In order to evaluate all the effects at the same scale (values between 0-1), a persistence parameter and a booster effect parameter will be calculated for HI and MN:

- Persistence index = $(MGI - 4)/MGI$ for each group.
- Boostability index = $(MGI - 4)/MGI$ for each group.

If the MGI value is less than 4, the index will be set to 0, the immunogenicity- fever, persistence and boostability indices will be ranked for each vaccine group.

Given the complexity of possible outcomes, an algorithm for dose selection will **not** be proposed.

Dose selection will be based on Day 42 immunogenicity and fever as key indicator of reactogenicity, persistence of the immune response and anamnestic response to unadjuvanted antigen as well as any additional safety concerns. Additional practical matters related to the estimated incremental benefit versus the complexity of a pediatric specific dosing regimen, should it not be a fraction of the adult dose, will also be weighed for dose selection as this could lead to increased complexity from a manufacturing and delivery perspective in a pandemic response setting.

8. CONDUCT OF ANALYSES

8.1. Sequence of analyses

8.1.1. ISRC analyses

iSRC (independent Safety Review Committee) analyses based on TVC are currently performed for the purposes of safety data review. These analyses were described in detail in a separate SAP/TFL associated to iSRC Charter.

8.1.2. Analysis at Day 42

An analysis will be performed on data collected through the Day 42 visit. Elements will include:

- An analysis of cleaned immunogenicity and solicited AEs data collected through the Day 42 visit will be conducted.
- Analyses of unsolicited AEs reported up to the Day 42 visit and cleaned in so far as is possible will be carried out.
- Analyses of MAEs, AESIs, SAEs, pIMDs and withdrawals due to AEs collected up to the Day 42 visit will be carried out.
- Results will be presented in a Day 42 statistical report. Access to individual treatment codes will be restricted to the designated statisticians in charge of the analysis. No individual listings or data with the subjects' identifying information will be disseminated. Listings of final data will be provided with the Day 415 report.

8.1.3. Final analysis

A final data analysis will be performed at the end of study (Day 415) of all primary and secondary endpoints based on the clean data, including evaluations of:

- demography and baseline characteristics
- immunogenicity
- solicited AE data (Day 0-6) after each vaccination
- unsolicited AEs reported up to the Day 42 visit (21 days after each dose), as well as 30 days after the Day 385 booster dose
- concomitant medications reported up to the Day 42 visit, as well as 30 days after the Day 385 booster dose
- MAEs, AESIs, SAEs, pIMDs and withdrawals due to AEs collected throughout the entire study.

Results of the final analysis, as well as individual data listings, will be presented in a final, integrated clinical study report (CSR).

